5.4 Statistical analysis

5.4.1 Sample size

The number of sample cases required for the study was estimated by two sample content calculation using physical activity as the outcome measure. Taking the medium and high intensity physical activity of the study subjects as the observed outcome indicator, according to the results, the mean and standard deviation of physical activity minutes of the control group was 35.88 ± 50.39 , the mean and standard deviation of the experimental group was 166.19 ± 116.92 , and the test level was set at 0.05 and the control was 90%. Calculate the formula according to the sample size:

$$n = \frac{(Z_\alpha + Z_\beta)^2 * 2\sigma^2}{\delta^2}$$

We calculated 20.8621 subjects in the experimental group and the control group, considering 20% lost to follow-up, so $n_1=n_2=21/0.8=26.2527$ cases. At least 27 subjects were needed in the experimental and control groups.

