The Effects of Parent-Child Activity Program on Physical Activity of Children With Cancer

March 31, 2024

1. Summary

Study Population: Children diagnosed with malignant tumors aged 6 to 14 years.

Outcome measures: ① Main outcome measures: physical activity behavior in children with cancer; ② secondary outcome indicators: height, weight, BMI, body fat, muscle, self-efficacy of physical activity, physical activity enjoyment, perceived social support in physical activity, and physical activity of parents.

Study Intervention: ① Control group: the children and their parents receive routine care and health education guidance, receive physical activity guidelines and suggestions for patients with malignant tumors provided by the researchers, and issue health knowledge education manual. In addition, the researchers and other members of the intervention team do not provide information about parent-child activities; ② Experimental group: the experimental group receives online and offline family-based parent-child physical activity intervention. It includes participating in offline group parent-child activities during hospitalization, including family competitive games and knowledge contests, etc., popularizing science of physical activity and parent-child sports activities to children and parents regularly after discharge, and pushing tweets, sports and practice videos related to physical activities and parent-child sports activities. Exercise were followed every 4 weeks and assessed for the previous session. The intervention protocol lasts 12 weeks and is followed up 3 months after the intervention is completed.

Sample size: with physical activity as the outcome indicator, the sample content was used to estimate the sample content calculation method, and the test level α was set to

0.05, and the control degree was 90%. According to the results of the literature review, 20.8621 subjects in the experimental group and the control group, considering 20% lost to follow up, so at least 27 subjects in the experimental group and the control group.

2. Introduction

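### The stated 20.8621 per group does not follow from the printed formula and inputs at 90% power; they give 16.92 or 10.03, depending on the SD used

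*Combined protocol and SAP*

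**What the plan says.** Section 5.4.1 takes minutes of medium and high intensity physical activity as the outcome. It uses the formula n = (Z_α + Z_β)² · 2σ² / δ², with these inputs:

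- Control group: "the mean and standard deviation of physical activity minutes of the control group was 35.88 ± 50.39".
- Experimental group: "the mean and standard deviation of the experimental group was 166.19 ± 116.92".
- Error rates: "the test level was set at 0.05 and the control was 90" per cent.

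The result is "We calculated 20.8621 subjects in the experimental group and the control group". The 20% loss to follow-up is then applied as "n_1=n_2=21/0.8=26.2527", and the section concludes: "At least 27 subjects were needed in the experimental and control groups".

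The Summary repeats the 90% ("the control degree was 90" per cent) and the result: "According to the results of the literature review, 20.8621 subjects in the experimental group and the control group". Neither place says which SD served as sigma, whether the test is one- or two-sided, or which Z values were used.

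**The concern.** The formula has a single sigma, but two quite different SDs are printed, so the result depends on a choice the plan does not state. The first question is whether any reasonable choice of sigma and sidedness gives 20.8621 at 90%. If none does, the power, an input or the result is wrong.

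This is the trial's only sample size calculation and it is printed twice. If its parts do not agree, a reader cannot tell what power the trial was sized for, or whether a mean or SD was misprinted. A misprinted input would matter most, because the adequacy of 27 per group would then have to be checked again.

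**Working it through.** **Inputs (section 5.4.1).** δ = 166.19 − 35.88 = 130.31 minutes, so δ² = 16,980.70. Test level 0.05. The 90% is read as power, because the formula needs a Z_β and no other printed figure could supply it. Sigma is not stated; the two natural candidates are:

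- larger SD: 116.92, giving 2σ²/δ² = 2 × 13,670.29 / 16,980.70 = 1.6101
- root-mean-square SD: √[(50.39² + 116.92²)/2] = 90.03, giving 2σ²/δ² = 0.9546

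**Attempt to reproduce 20.8621 at 90%.** Two-sided, (1.960 + 1.2816)² = 10.507. One-sided, (1.645 + 1.2816)² = 8.564.

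| Sigma | Two-sided n per group | One-sided n per group |
|---|---|---|
| 116.92 (larger SD) | 16.92 | 13.79 |
| 90.03 (root-mean-square) | 10.03 | 8.17 |
| 83.66 (mean of the SDs) | 8.66 | 7.06 |
| 50.39 (smaller SD) | 3.14 | 2.56 |

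The stated figure is not reproduced.

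**What would be needed at 90%.** Solving for sigma, σ = √[20.8621 × 16,980.70 / (2 × 10.507)] = 129.8 two-sided, and 143.8 one-sided. Both exceed 116.92. So the missing statements on sigma and sidedness do not explain the gap.

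**Power implied by 20.8621 with the larger SD.** Z_α + Z_β = √(20.8621 / 1.6101) = 3.5996.

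- Two-sided: Z_β = 3.5996 − 1.960 = 1.640, which is 94.9% power.
- One-sided: Z_β = 3.5996 − 1.645 = 1.955, which is 97.5% power.

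**Possible origin.** (1.96 + 1.64)² × 1.6101 = 20.87; with 1.645 in place of 1.64 it is 20.92. Both are close to 20.8621, but neither is exact. With the root-mean-square SD, 1.96 + 1.64 gives only 12.37, so the near-match needs the larger SD.

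**Power at 21 evaluable per group, two-sided.** With SD 116.92 in both arms: 95.1% by normal approximation, 94.1% by t-test. With SD 90.03: 99.7% and 99.6%.

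**Allowance for 20% loss.**

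- Stated figures: 21/0.8 = 26.25 and 20.8621/0.8 = 26.08. The printed 26.2527 × 0.8 = 21.0022, which is neither 21 nor 20.8621. All of these round up to 27.
- Formula at 90%, two-sided: 17/0.8 = 21.25, so 22 per group (larger SD); 11/0.8 = 13.75, so 14 per group (root-mean-square SD).

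**The case against.** The strongest objection is that the error does no harm. At 90% a t-test needs 18 per group with the larger SD or 12 with the root-mean-square SD. After 20% loss these become 23 (18/0.8 = 22.5) and 15 (12/0.8 = 15), still below 27. This stands: on the printed inputs, neither enrolment nor the analysis changes. It limits the weight of the point but does not reconcile the figures.

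A second objection is that 95% power is only a guess at the cause. This also stands. The figure assumes a two-sided test, whereas the plan prints Z_α and gives no sidedness; one-sided, the same Z sum means 97.5% power. A wrong sigma is another route. Setting σ² to the sum of the two variances while keeping the factor 2 gives 20.06 at 90%. That counts the variance twice and does not match the printed decimals, so it is not a reproduction, but it shows that the slip may lie elsewhere. A misprinted mean or SD is also possible, in which case 90% could be correct.

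A third objection is that the word used in the plan may not mean power. If it does not, the calculation has no stated power and still needs correcting.

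Finally, a higher printed power could mislead in a non-randomised study with sequential groups, analysed by mixed-design ANOVA or GEE. That is a fair caution about how any restated figure is labelled.

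**Conclusion.** The concern holds. As printed, 90% power and 20.8621 per group cannot both be right with the printed means and SDs, under either sidedness and with any common SD up to 116.92. With the larger SD the discrepancy is 17 against 21 evaluable per group, or 22 against 27 after loss, about 1.2-fold. With the root-mean-square SD it is 11 against 21, or 14 against 27.

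The direction is conservative: on these inputs 90% understates the power at 21 per group, which is about 94–95% two-sided with the larger SD in both arms, and higher with a smaller SD or a one-sided test. What is at stake is reproducibility and the power statement, not the number enrolled.

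These power figures are approximate two-sample values at one time point and assume normal data. The control SD (50.39) exceeds its mean (35.88), so the minutes are probably right-skewed and the figures are a rough guide. They are not the power of the planned mixed-design ANOVA or GEE. The arithmetic mismatch does not depend on the distribution. The origin of 20.8621 remains unknown. The slip in the dropout division has no effect on 27.

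**What to change.** Keep at least 27 per group. State which SD is sigma, whether the test is one- or two-sided, the two Z values used, and that the 90% means power. Check the sponsor's own calculation, Z_β first and then the means and SDs, and correct whichever item is wrong in both the Summary and section 5.4.1:

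- **If the inputs and 20.8621 (21 per group) stand:** restate the power as about 94–95% or higher (two-sided, larger SD in both arms). Label it as an approximate two-sample figure at one time point that assumes normal data, not the power of the mixed-design ANOVA or GEE.
- **If 90% stands:** print 16.92 (17 per group) or 10.03 (11 per group) for a two-sided test, according to the sigma used, as the normal-approximation requirement. Note that 27 exceeds it after 20% loss. If the test is one-sided, use the corresponding 13.79 or 8.17.
- **If a mean or SD was misprinted:** rerun the formula with the corrected value and confirm that 27 still covers it.

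In every case print 21/0.8 as 26.25.

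The cost is a text correction in two places and one look at the original calculation. On the printed inputs there is no change in enrolment.

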5.4.2 Statistical Analysis

The Epidata3.1 database was established, the data was entered by two people, and the SPSS25.0 statistical software was used for statistical analysis, and the test level was set at $\alpha = 0.05$.

(1) Description statistics: ① Data following normal distribution are described by mean and standard deviation; ② data without normal distribution are described by median and interquartile spacing.

(2) Data analysis: (3) Use Excel to establish the database, double input data, and use SPSS25.0 statistical software for statistical analysis, as follows:

① Using frequency, composition ratio, mean, standard deviation to describe the general data of children with tumors and their parents, the disease data of children and other conditions;

② The t-test, chi-square test or rank sum test were balanced for general data, physical activity, physical activity self-efficacy, physical activity enjoyment, and physical activity social support between the experimental and control groups.

③ One-way repeated measures analysis of variance was used to compare the number of high intensity physical activity minutes between children and parents in the experimental group.

④ If the data of physical activity, physical activity self-efficacy, physical activity enjoyment and physical activity social support meet the normal distribution (Shapiro-Wilk test) and equal variance (scatter plot), the mixed design analysis of variance shall be used to intervene the effects of main effect, time main effect, intervention time effect and confounding factors; if not satisfied, the generalized

estimation equation is used.

6. Research intervention

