5.1 Overall design

5.1.1 Study Hypotheses

- (1) The physical activity of most children with cancer does not meet the guidelines suggest that their physical activity is positively related to self-efficacy, enjoyment, family support and the physical activity of their parents;
- (2) Compared with the control group, parent-child activity intervention can improve the physical activity of children with cancer and their parents, promote the self-efficacy and physical enjoyment of physical activity, and enhance the family support of children.

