5.1.2 Study design

This study is a class of experimental study. The pediatric malignant tumor patients and

the parents were selected by convenience sampling.

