5.2 Study design process

Establish an intervention team composed of researchers and qualified doctors and nurses, and evaluate the intervention members. Study subjects were recruited according to the exclusion criteria, and after obtaining informed consent and signing the consent form, the study subjects were included in the control group and experimental group. In order to prevent contamination, it was divided into control group and experimental group according to the chronological order, that is, the experimental group was included first, and in the experimental group, the control group was included after the sample size is sufficient. The control and experimental groups received usual care and parent-child activity intervention. Data were collected and analyzed at enrollment (T0), 1 month (T1), 2 months (T2), 3 months (T3), and 3 months (T4) after the intervention.

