5.3 Methods to reduce the bias

- (1) Adopt the research method of similar experiment, collect all the data of the experimental group, and then recruit the control group to collect the data to avoid the occurrence of contamination;
- (2) The intervention team members shall receive unified physical activity training and assessment before the intervention, jointly propose the possible situation during the implementation of the intervention, unify the interpretation method of the questionnaire items, and give unified language answers to the questions about the questionnaire;

(3) In the process of collecting the questionnaire, collect the questionnaire on the spot, evaluate and check the completion of the questionnaire, timely find and correct the missing contents, ensure the integrity and effectiveness of the questionnaire information, and timely input the data after collecting the questionnaire;

(4) When analyzing the data, check the integrity and validity of the data again, and make remedial plan for the incomplete questionnaire; establish a database, and two people jointly input and check the data to ensure the accuracy of data entry.

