- ① WeChat group communication, enhance the information interaction and emotional support between peers.
- ② Family competition, improve the role of role model.

III . Strengthen the role of medical staff —— Medical staff support

- ① Information and technical support: medical staff shall provide relevant information, venues and goods to the child and their parents.
- ② Emotional support: When children and parents have problems or emotional needs, intervention team members should provide timely answers and encouragement online; at monthly follow-up, researchers will provide separate face-to-face interviews to help them solve their problems.
- ③ Other support: In the offline activities, the medical staff also actively participate in the demonstration for the children and their parents.

(3) The intervention program lasts for 12 weeks and is follow-up for 3 months after the completion of the intervention.

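### Item (4) of section 5.4.2 does not say whether the group main effect, which averages over T0, or the group-by-time effect decides hypothesis (2), so a stable difference between the sequential cohorts could be reported as an intervention effect

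*Combined protocol and SAP*

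**What the plan says.** Hypothesis (2) in section 5.1.1 is comparative: "Compared with the control group, parent-child activity intervention can improve the physical activity of children with cancer and their parents", with self-efficacy, enjoyment and family support alongside. The between-group analysis is section 5.4.2, item (4): if normality and equal variance hold, a "mixed design analysis of variance shall be used to intervene the effects of main effect, time main effect, intervention time effect and confounding factors". Beside the other two terms, the unqualified main effect can only be that of the intervention. The fallback ("if not satisfied, the generalized" estimating equation) is named without a link, visit coding or deciding term.

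On visits, section 5.2 states: "Data were collected and analyzed at enrollment (T0), 1 month (T1), 2 months (T2), 3 months (T3), and 3 months (T4) after the intervention". Section 7 treats T0 as baseline.

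On how the groups arise, section 5.1.2 says that the patients and "the parents were selected by convenience sampling". Section 5.2 assigns them by calendar order: "the experimental group was included first, and in the experimental group, the control group was included after the sample size is sufficient". Section 5.3, item (1), goes further: "collect all the data of the experimental group, and then recruit the control group to collect the data".

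Item (2) of section 5.4.2 tests the groups for balance, but no consequence is attached to an imbalance. The confounders in item (4) are not named, and no section makes the T0 value a covariate.

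**The concern.** The two between-group terms answer different questions. The group-by-time effect asks whether the groups changed differently. The group main effect asks whether they differ on average over all visits, one of which precedes the intervention. In a randomised trial, including T0 would mainly dilute the main effect. Here the groups come from different calendar periods by convenience sampling, so they may differ from the start in diagnosis mix, treatment phase or season. Such a difference, if stable, is carried whole into the main effect.

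At stake is the trial's comparative claim. A term that the plan itself lists can be significant with no intervention effect, and the choice of term is left open until the data are seen.

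**Working it through.** **Inputs from the documents.** Section 5.4.1 gives 35.88 ± 50.39 minutes (control), 166.19 ± 116.92 (experimental), 21 per group, and 27 after 20% loss. The plan's own 20.8621 does not follow from its printed formula: at two-sided 0.05 and 90% power, with difference 130.31, I get 16.92 using SD 116.92 and 10.03 using the root-mean-square SD. The loss step is sound (21/0.8 = 26.25, so 27). That is a separate matter; I take 21 and 27 as given.

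**Assumed, not in the documents.** Two-sided 0.05; normal data with unit SD in both groups; equal correlation r between visits (0.3, 0.5, 0.7); no confounder adjustment; a constant cohort offset D.

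**Step 1, algebra.** Let the group difference at visit t be D + e_t, with e_0 = 0 before the intervention.
- Five-visit main effect: D + (e_1 + e_2 + e_3 + e_4)/5.
- T3 minus T0 contrast: (D + e_3) − D = e_3.

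With no intervention effect, the first equals D and the second equals 0, for any D.

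**Step 2, size.** The SD of a child's five-visit mean is √((1+4r)/5) = 0.663, 0.775, 0.872. For D = 0.5 and n = 21, the noncentrality D/(SD × √(2/21)) is 2.44, 2.09, 1.86 on 40 df. How often the main effect is significant with no intervention effect:

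| Offset D, n per group | r = 0.3 | r = 0.5 | r = 0.7 |
|---|---|---|---|
| 0.2 SD, 21 | 16% | 13% | 11% |
| 0.3 SD, 21 | 30% | 23% | 19% |
| 0.5 SD, 21 | 66% | 53% | 44% |
| 0.8 SD, 21 | 97% | 90% | 83% |
| 0.5 SD, 27 | 78% | 64% | 54% |

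Family support is collected at three visits only (T0, T3, T4). There the SD is √((1+2r)/3), and D = 0.5 with n = 21 gives 58/49/42%. In simulation, the change-from-T0 contrasts and the ANOVA interaction test stay at 4.7% to 5.3%.

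**Step 3, would the balance test warn?** At n = 21 a T0 t-test detects a 0.5 SD offset about 35% of the time. In 34% to 13% of trials (r = 0.3 to 0.7), the balance test is non-significant and the main effect significant.

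**Step 4, the GEE fallback.** If the section 5.4.1 figures describe the trial data, this branch is likely. The variance ratio is (116.92/50.39)² = 5.4, and a normal variable with mean 35.88 and SD 50.39 would be negative in about 24% of children. With an identity link a stable offset still cancels from the change contrast. With T0 as reference visit, the group coefficient is the T0 difference, not a five-visit average, so the Step 2 rates do not apply. In simulation with no intervention effect, uncorrected robust Wald tests at 21 to 27 per group reject in about 6% to 7% for a single contrast. For the 4-df interaction they reject in about 9% to 13%, highest at n = 21 with the unequal SDs.

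**Step 5, power of T3 minus T0.** Its SD is √(2(1−r)) = 1.18, 1.00, 0.775. A constant effect at T1 to T4 enters the main effect at 4/5 of its size. The two tests have equal power when (1+4r)/5 = 0.64 × 2(1−r), that is r = 1.08/2.08 = 0.52. For the section 5.4.1 difference on its larger SD (130.31/116.92 = 1.11 SD, n = 21), power at r = 0.3/0.5/0.7 is 85/94/99.5% for T3 minus T0 and 99/95/90% for the main effect.

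**Step 6, drift.** Suppose the cohorts are equal at T0 and drift apart by 0, 1/6, 1/3, 1/2, 1/2 SD at T0 to T4. T3 minus T0 then carries 0.5 SD and the five-visit mean 0.3 SD. False positives at n = 21 are 27/35/53% for T3 minus T0 and 30/23/19% for the main effect.

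**The case against.** The word improve in hypothesis (2) fits the group-by-time effect, and a careful analyst would probably use it. The stated main purpose (section 3.1.1) is to construct the programme, and section 3.1.2 only explores its effect. Both points stand as to likelihood and weight, but neither ties the claim to a term.

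The rates rest on an assumed offset, constant over time, in the five-visit normal ANOVA without adjustment. This stands: the documents give no offset and no visit correlation, item (4) does mention confounders, and the GEE may well be the analysis used.

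The change contrast is not always safer. This stands too: under drift it does slightly better than the main effect at r = 0.3 and much worse at r = 0.7.

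Three stronger readings are tempting. A reader might infer that the plan decides on the main effect and so has a false-positive rate of 44% to 66%; the plan does not choose that term, and nothing shows that the cohorts differ by 0.5 SD. A reader might infer that a change contrast cures the confounding; it removes only the stable part. A reader might infer from section 5.3, with "The intervention program lasts for 12 weeks and is follow-up for 3 months after the completion of the intervention" in section 6.1, that controls start at least 12 weeks plus 3 months after the last experimental child enrols. Section 5.2 requires only that the experimental sample be complete, which permits a shorter gap.

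**Conclusion.** The concern holds in limited form and should be fixed before analysis. What rests on the text and algebra alone is that no deciding term is named, that the listed main effect includes T0, and that a stable cohort difference passes into it undiminished while cancelling from change since T0. The size is illustrative and conditional on the assumptions above. The defect is an open choice that could mislead, not a planned error. The underlying confounding by calendar order is a design limit that analysis wording cannot remove.

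**What to change.** In section 5.4.2, for both the mixed ANOVA and the GEE, name the group difference in change from T0 to T3 in the child's moderate-to-vigorous minutes as the single deciding test of hypothesis (2). Section 5.4.1 already uses that outcome. By section 7, T3 is the only post-baseline visit with every hypothesis (2) outcome: family support is absent at T1 and T2, self-efficacy and enjoyment at T4. Also:

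- Make all other contrasts secondary.
- State that a group term that includes T0, or is coded at T0, is not evidence of efficacy.
- For the GEE, specify an identity link, T0 as reference visit, and a small-sample correction to the robust standard errors.
- State as a limit that calendar-period change during follow-up is not removed, and that conclusions remain those of a non-randomised sequential comparison.
- Reconcile sections 5.2 and 5.3 on when control recruitment starts.

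Adding T0 only as a covariate would not be enough: in simulation (0.5 SD offset, n = 21, no intervention effect), covariance analysis of the post-T0 mean still rejected in 39/23/13% of trials at r = 0.3/0.5/0.7.

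The cost is wording, with no added visits or participants, and some power. For a constant effect, T3 minus T0 is weaker than the main effect at correlations below about 0.52, and at 0.3 it reaches 85% against the stated 90%.
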